### 9.2.2 Analysis of Variance

For the analysis of quality of life variables, on the absolute change from baseline for each score, the mean treatment differences for each ACT-334441 dose compared to placebo and their corresponding 95% confidence intervals are provided using a One-way analysis of variance (ANOVA) with treatment group as a factor in the model.

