**Figure 2 Dose-response curves considered in MCP-Mod procedure**

The null hypothesis of 'no dose-response' will be rejected if at least one of the five multiple comparison tests has an adjusted p-value  $< 0.05$ . All statistically significant models (i.e., with a multiplicity adjusted p-value  $< 0.05$ ) are fitted in the Mod step and for each model Akaike's Information Criterion (AIC) is calculated. The smaller the value of AIC (= model deviance + 2 times the number of model parameters), the better the fit. The analysis is performed using the R-package *DoseFinding* [Bornkamp 2016].

The basic R-code is similar to:

```
library(DoseFinding)
doses <- c(0, 0.5, 1.0, 2.0, 4.0)
s <- sEmax(ed50=0.4, ed95=2)
candMod <- Mods(
  emax = c(0.2, 0.4, 1.0),
  sigEmax = s,
  quadratic = -0.167,
  doses = doses,
  placEff = 0,
  maxEff = -70% reduction from of the mean baseline value,
  direction = "decreasing"
)
MMfit <- MCPMod(
  dose = TRTDOSEP,
  resp = CHG,
  data = LYM,
  addCovars = ~BASE,
  models = candMod,
  delta = -1.4(arbitrary to run model, target dose not estimated)
)
```

In the *Mods* function call the candidate models are specified, together with the assumed placebo and maximum effects. In the call to the *MCPMod* function, LYM is a data frame with objects TRTDOSEP (Planned Dose for Period 01), CHG (for Absolute change from baseline), and BASE (for Baseline Value) and delta is a target difference vs. placebo. The object *MMfit* is summarized to obtain the MCP test, parameter estimates, target dose and AIC. These elements go in a summary table. The object is plotted to display the fitted dose-response curves.

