#### Statistical considerations

In analysis of variance, a continuous response variable, known as a *dependent variable*, is measured under experimental conditions identified by classification variables, known as *independent variables*. The variation in the response is assumed to be due to effects in the classification, with random error accounting for the remaining variation.

Adjusted means are calculated by fitting the following fixed effects analysis of variance (ANOVA) model,

$$Y_{ik} = \mu + \alpha_i + \varepsilon_{ik}$$

where

- $Y_{ik}$  is the absolute change from baseline of the  $k^{\text{th}}$  subject in treatment group  $i$ ;
- $\mu$  is the overall mean;
- $\alpha_i$  is the main effect of treatment group  $i$ ;

- $\varepsilon_{ik}$  are error terms which are normally distributed with a mean of zero and variance  $\sigma^2$  ( $\varepsilon_{ijk} \sim N(0, \sigma^2)$ ).

*Validation:*

The normal distribution of the variables is evaluated by means of the Shapiro-Wilk test and graphically (stem and leaf plot and normal probability plot) in each treatment group. The homogeneity of variances across treatment groups is assessed using Hartley's test.

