#### *SAS Code*

The SAS statements used to calculate the means and the between-group differences are similar to:

```
ods output ESTIMATES = DIFF;
ods output LSMeanCL = LSM;

proc glm data = changes ;
  by TESTNO TESTCD TEST ;
  class TRTGRPPS;
  model CHANGE = TRTGRPPS/ss3;
  lsmeans TRTGRPPS / tdiff stderr cl;

  estimate "Group A minus Group E" TRTGRPPS 1 0 0 0 -1;
  estimate "Group B minus Group E" TRTGRPPS 0 1 0 0 -1;
  estimate "Group C minus Group E" TRTGRPPS 0 0 1 0 -1;
  estimate "Group D minus Group E" TRTGRPPS 0 0 0 1 -1;

run;
quit;
```

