#### **9.2.3 Analysis of Covariance**

For analyses involving the absolute and/or the percent changes from baseline for a studied parameter, the mean treatment differences for each ACT-334441 dose compared to placebo and their corresponding 95% confidence intervals are provided using an Analysis of Covariance (ANCOVA) including baseline value as a covariate and with treatment group as a factor in the model.

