### *SAS Code*

The SAS statements used to calculate the adjusted means and the between-group differences are similar to:

```
ods output ESTIMATES = DIFF;
ods output LSMeanCL = LSM;

proc glm data = changes ;
  by TESTNO TESTCD TEST ;
  class TRTGRPPS;
  model CHANGE = TRTGRPPS BASELINE /ss3;
  lsmeans TRTGRPPS / tdiff stderr cl;

  estimate "Group A minus Group E" TRTGRPPS 1 0 0 0 -1;
  estimate "Group B minus Group E" TRTGRPPS 0 1 0 0 -1;
  estimate "Group C minus Group E" TRTGRPPS 0 0 1 0 -1;
  estimate "Group D minus Group E" TRTGRPPS 0 0 0 1 -1;

run;
quit;
```

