### **10.10 Analysis of quality of life variables**

For each score (8 domain scores, 2 component scores), quantitative descriptive statistics are presented for each analysis visit (baseline and EOT) and for the change from baseline to EOT by treatment group for the SAF. Additionally, the mean treatment differences for each ACT-334441 dose compared to placebo and their corresponding 95% CIs are provided using an ANOVA with treatment group as a factor in the model.

If the data are non-normally distributed or should the assumptions underlying the ANOVA model (normality of the residuals, homogeneity of the variance) not be fulfilled, the same comparisons between treatment groups will also be performed using a non-parametric one-way ANOVA.

For the reported health transition item, qualitative descriptive statistics are presented for each visit by treatment group.

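### The SF-36v2 comparisons with placebo leave out the baseline score, although every other modelled change from baseline in the SAP adjusts for it

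*SAP*

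**What the plan says.** SAP 9.2.2 is written for the quality of life variables. For the absolute change in each score it states that the differences from placebo and their 95% "confidence intervals are provided using a One-way analysis of variance (ANOVA) with treatment group as a factor in the model". The model equation has an overall mean, a treatment effect and an error term. It is introduced with the words "Adjusted means are calculated by fitting the following fixed effects analysis of variance (ANOVA) model", and the SAS line is "model CHANGE = TRTGRPPS/ss3". SAP 10.10 repeats the treatment-only ANOVA. If its assumptions fail, 10.10 adds that "the same comparisons between treatment groups will also be performed using a non-parametric one-way ANOVA".

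SAP 9.2.3, the next section, opens "For analyses involving the absolute and/or the percent changes from baseline for a studied parameter" and prescribes an ANCOVA "including baseline value as a covariate and with treatment group as a factor in the model". Its SAS line is "model CHANGE = TRTGRPPS BASELINE /ss3". It makes no exception for quality of life.

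SAP 5.9 has the questionnaire completed at Visit 2 (Day 1) and at Visit 6 (EOT), so a baseline score is collected.

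**The concern.** Two adjacent sections of the SAP give different models for the same kind of variable. SF-36v2 is the only endpoint for which a modelled comparison of change with placebo omits baseline. SAP Section 4, which lists changes and clarifications, does not mention it. The phrase about adjusted means in 9.2.2 does not describe what the model does: with treatment as the only term, the estimates are the raw arm means.

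What is at stake is precision. When the correlation between baseline and EOT is below one, an arm that happens to start low tends to show a larger rise whatever it received. An analysis of change without baseline carries that into the estimate as noise. With about 12 subjects per dose and 16 on placebo, chance differences at baseline will be common.

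**Working it through.** **Models side by side (SAP).**

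| Endpoint (change from baseline v placebo) | Section | Baseline in the model? |
|---|---|---|
| Lymphocytes, MCP-Mod | 9.2.1 | Yes, "addCovars = ~BASE" |
| Lymphocytes, pairwise, absolute and % change | 10.6.3 | Yes |
| Lymphocytes, separate Part A and Part B ANCOVAs | 10.6.4 | Yes |
| SLEDAI-2K scores, affected joints, PGA | 10.8.1.1 | Yes |
| SF-36v2 domain and component scores | 9.2.2, 10.10 | No |

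Biomarkers, ECG, blood pressure, spirometry, laboratory values and body weight are summarised descriptively, so they are outside the comparison.

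**Inputs.** Protocol 11.6.1 gives 12 subjects on each of four doses and 16 on placebo: N = 64, k = 5 arms. The documents give no SF-36v2 standard deviation, correlation or power, so there is no stated figure to reproduce. I assume equal variance s² at baseline and EOT, and show r as a range.

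**Formulas.**
- Variance of the change score (ANOVA): 2s²(1 − r), on 64 − 5 = 59 df.
- Residual variance given baseline (ANCOVA): s²(1 − r²), on 58 df.
- Estimating the slope inflates the ANCOVA variance on average by 1 + 1/(N − k − 2) = 1 + 1/57.
- Expected ratio of CI widths, ANOVA to ANCOVA: √(2/(1 + r)) / √(1 + 1/57). The t quantiles on 59 and 58 df are nearly equal.

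At r = 0.5: √(2/1.5) = 1.155, and 1.155/1.009 = 1.145.

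**Chance imbalance.** The standard error of a baseline difference, 12 v 16, is √(1/12 + 1/16) = 0.382 baseline SD. A baseline difference of that size moves the unadjusted estimate by (1 − r) × 0.382 SD.

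| r (assumed) | Width ratio, formula | Width ratio, simulated | Equivalent increase in N | Shift from a one-SE baseline difference (SD) |
|---|---|---|---|---|
| 0.3 | 1.230 | 1.230 | 51% | 0.267 |
| 0.5 | 1.145 | 1.143 | 31% | 0.191 |
| 0.7 | 1.075 | 1.074 | 16% | 0.115 |
| 0.8 | 1.045 | 1.044 | 9% | 0.076 |
| 0.9 | 1.017 | 1.017 | 3% | 0.038 |
| 0.95 | 1.004 | 1.004 | 1% | 0.019 |

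The simulated ratios come from 6,000 trials per value of r with the planned arm sizes. With 11 per dose and 14 on placebo (an assumed loss of about 10%) they are 1.229, 1.142, 1.073 and 1.016 at r = 0.3, 0.5, 0.7 and 0.9.

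**Break-even.** The ratio equals 1 when 1 + r = 2/(1 + 1/57), which gives r = 0.966. Above that ANCOVA is wider, but trivially: at r = 0.97 its simulated width is 1.001 times that of ANOVA.

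**Bias.** In a separate simulation of 4,000 trials per r, neither method was off by more than 0.01 SD on average.

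**How common is imbalance?** For any one score, the chance that at least one of the four doses differs from placebo at baseline by 0.382 SD or more is about 73% (200,000 simulated trials).

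**The case against.** Section 9.2.2 is an explicit provision for quality of life, and its text, equation, code and Section 10.10 all agree. A specific rule would normally prevail over the general wording of 9.2.3. That stands: this is not a coding slip but an unexplained difference between two sections.

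Nor is it a clear departure from the protocol. Protocol 11.4.4 sends other changes from baseline to ANCOVA, but under an efficacy heading and without naming SF-36. Protocol 11.3.6 introduces SF-36v2 as a disease activity variable, but that lead-in may have been carried over from 11.3.5. The protocol is supportive at most.

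The change-score ANOVA is valid, the endpoint is exploratory, and the gain depends on an unknown r. All true.

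The imbalance argument largely restates the loss of precision, because that variation is already inside the ANOVA standard error. This also stands. A one-SE baseline difference moves the estimate by √((1 − r)/2) of its own SE, which is 0.59, 0.50, 0.39 and 0.22 at r = 0.3, 0.5, 0.7 and 0.9. The 73% should be read as a description of how common imbalance is, not as a second harm.

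Finally, the SAP contains no method for a baseline-adjusted non-parametric fallback, and ANCOVA assumes a common linear slope across small arms on bounded scores. So only the parametric change is nearly free. None of these points is a reason to leave out a covariate that the SAP uses everywhere else.

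**Conclusion.** The concern holds. SF-36v2 is the only modelled change-from-baseline comparison with placebo in the SAP that omits baseline, and no reason is given. Under the assumptions of equal variances and r between 0.3 and 0.9, the planned intervals are about 23% to 2% wider than they need be, with no gain beyond r of about 0.97.

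The planned analysis is unbiased over randomisation, and no pharmacodynamic or safety conclusion depends on it. One contrast deserves a note: the 4 mg arm comes only from Part B, while 12 of the 16 pooled placebo subjects come from Part A, so baseline differences there are not purely chance. Adjustment deals only with the part carried by the baseline score. This is a worthwhile, low-cost improvement to an exploratory analysis, not a correction of an error.

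**What to change.** In SAP 9.2.2 and 10.10, replace the one-way ANOVA with the 9.2.3 model, change = treatment + baseline score, for the eight domain and two component scores, using "model CHANGE = TRTGRPPS BASELINE /ss3". The label of adjusted means then becomes accurate. Make the change before treatment codes are released, and record it in Section 4.

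The cost is one model term already coded in the SAP and one residual degree of freedom (59 to 58). Data collection and the analysis set are unchanged.

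Optionally, adjust the non-parametric fallback for baseline as well where feasible. The SAP would need to add a method for this. If the sponsor prefers to keep the unadjusted model, Section 4 should state why SF-36v2 is exempt from 9.2.3. That would settle the inconsistency but not recover the lost precision.

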#### Statistical considerations

In analysis of variance, a continuous response variable, known as a *dependent variable*, is measured under experimental conditions identified by classification variables, known as *independent variables*. The variation in the response is assumed to be due to effects in the classification, with random error accounting for the remaining variation.

Adjusted means are calculated by fitting the following fixed effects analysis of variance (ANOVA) model,

$$Y_{ik} = \mu + \alpha_i + \varepsilon_{ik}$$

where

- $Y_{ik}$  is the absolute change from baseline of the  $k^{\text{th}}$  subject in treatment group  $i$ ;
- $\mu$  is the overall mean;
- $\alpha_i$  is the main effect of treatment group  $i$ ;

- $\varepsilon_{ik}$  are error terms which are normally distributed with a mean of zero and variance  $\sigma^2$  ( $\varepsilon_{ijk} \sim N(0, \sigma^2)$ ).

*Validation:*

The normal distribution of the variables is evaluated by means of the Shapiro-Wilk test and graphically (stem and leaf plot and normal probability plot) in each treatment group. The homogeneity of variances across treatment groups is assessed using Hartley's test.

#### *SAS Code*

The SAS statements used to calculate the means and the between-group differences are similar to:

```
ods output ESTIMATES = DIFF;
ods output LSMeanCL = LSM;

proc glm data = changes ;
  by TESTNO TESTCD TEST ;
  class TRTGRPPS;
  model CHANGE = TRTGRPPS/ss3;
  lsmeans TRTGRPPS / tdiff stderr cl;

  estimate "Group A minus Group E" TRTGRPPS 1 0 0 0 -1;
  estimate "Group B minus Group E" TRTGRPPS 0 1 0 0 -1;
  estimate "Group C minus Group E" TRTGRPPS 0 0 1 0 -1;
  estimate "Group D minus Group E" TRTGRPPS 0 0 0 1 -1;

run;
quit;
```

#### **9.2.3 Analysis of Covariance**

For analyses involving the absolute and/or the percent changes from baseline for a studied parameter, the mean treatment differences for each ACT-334441 dose compared to placebo and their corresponding 95% confidence intervals are provided using an Analysis of Covariance (ANCOVA) including baseline value as a covariate and with treatment group as a factor in the model.

#### *Statistical considerations*

The model used for this analysis is a general linear model studying treatment effect with baseline value of studied parameter (as fixed effect) as covariate:

$$Y_{ik} = \gamma X_{ik} + a_i + \varepsilon_{ik}$$

where:

- $Y_{ik}$  is the response from the  $k^{\text{th}}$  subject that received treatment  $i$ ,
- $X_{ik}$  is the baseline value of the analysed variable for the  $k^{\text{th}}$  subject that received treatment  $i$ ,
- $\gamma$  denotes the common slope of the baseline covariate,

- $a_i$  denotes the intercept of the  $i^{\text{th}}$  treatment,
- $\varepsilon_{ik} \sim \text{iid } N(0, \sigma_{\varepsilon}^2)$  denotes the experimental unit error associated with the  $k^{\text{th}}$  subject that received treatment  $i$ .

The model can also be written in matrix notation as:

$$Y = X\beta + \varepsilon$$

where:

- $Y$  is the vector of observations,
- $X$  is the design matrix of the fixed effects and baseline factors,
- $\beta$  is the unknown vector of the fixed effects and baseline factors,
- $\varepsilon$  is the unobserved vector of independent and identically distributed random errors, such as  $\varepsilon \sim N(0, R)$  where  $R = \sigma_{\varepsilon}^2 \sigma_{\varepsilon}^2 \sigma_{\varepsilon}^2 I_n$ .

#### Estimations:

The estimate  $\hat{\beta}$  of  $\beta$  is given by:

$$\hat{\beta} = (X'X)^{-1} X'Y$$

with  $Var(\hat{\beta}) = (X' \hat{R}^{-1} X)^{-1} = \hat{C}$

#### Confidence interval:

The Sum of Squares (SS) using a LS-means contrast is used for computing  $SS_{(H0: L\beta = 0)}$  (where  $L\beta$  denotes a linear estimable combination of the fixed effects):

The 95% confidence interval of  $\hat{\beta}$  is given by:

$$L\hat{\beta} \pm t_{\hat{v}, 0.975} \sqrt{L\hat{C}L'}$$

where:

- $\hat{v}$  denotes the approximate degrees of freedom by Satterthwaite,
- $t_{\hat{v}, 0.975}$  is the 0.975th quantile of the t-distribution with  $\hat{v}$  degrees of freedom.

The least-squares approach provides estimates of the linear parameters that are unbiased and have minimum variance among linear estimators.

The treatment effect is estimated by the difference of the LS-means of each studied treatment group.

#### Validation:

Residual normality and homoscedasticity will be studied using graphs and descriptive statistics.

### *SAS Code*

The SAS statements used to calculate the adjusted means and the between-group differences are similar to:

```
ods output ESTIMATES = DIFF;
ods output LSMeanCL = LSM;

proc glm data = changes ;
  by TESTNO TESTCD TEST ;
  class TRTGRPPS;
  model CHANGE = TRTGRPPS BASELINE /ss3;
  lsmeans TRTGRPPS / tdiff stderr cl;

  estimate "Group A minus Group E" TRTGRPPS 1 0 0 0 -1;
  estimate "Group B minus Group E" TRTGRPPS 0 1 0 0 -1;
  estimate "Group C minus Group E" TRTGRPPS 0 0 1 0 -1;
  estimate "Group D minus Group E" TRTGRPPS 0 0 0 1 -1;

run;
quit;
```

## 10 STATISTICAL ANALYSES

This study is performed in two parts: part A with four treatment groups (including 0.5 mg, 1 mg, or 2 mg of ACT-334441 and placebo control) and part B with two treatment groups (including 4 mg of ACT-334441 and placebo control). In all analyses the assumption is made that the data from part A and part B can be combined, in particular the subjects randomized to placebo in any part of the study are analyzed as one group. This assumption is investigated for the main pharmacodynamics endpoint in a sensitivity analysis.

### 10.1 Overall testing strategy

An optimized contrast test according to the Multiple Comparison Procedure and Modeling (MCP-Mod) approach [Bretz 2005] for each considered dose-response model is performed. The existence of dose-response effects on the change from baseline in lymphocytes counts at EOT is tested using the maximum of the model-based contrast tests using a one-sided 0.05 alpha. Multiplicity adjusted p-values are calculated using the Dunnett-distribution which controls the type 1 error.

All other statistical testing are performed at a two-sided significance level of 0.05 using 95% Confidence Limits (CLs).

In all analyses of secondary and other efficacy variables, no correction will be made for multiple testing.

## 10.2 General rules for data presentations

This section describes the general rules applied for all data displays, unless otherwise specified in each corresponding section.

SAS version 9.4 is used for the preparation of all tables, listings and figures.

Listings are sorted by country, site, treatment group, subject number and timing (dates, times and/or visits as applicable) and will display all subjects.

Names of outputs begin with T for Table, F for Figure and L for Listing, the next 2 digits represent the ADaM dataset the output is based on (e.g. LB for laboratory), followed by a numerical number and finally there is a suffix that indicates the analysis set (e.g., SAF for Safety Analysis Set).

Data are listed and summarized using appropriate descriptive statistics:

- Number of non-missing observations, mean, standard deviation, minimum, Q1, median, Q3 and maximum for continuous variables.
- Number of non-missing observations, and frequency with percentage per category for categorical variables. Denominators for percentages are the number of subjects in the pertinent analysis set and treatment group, unless otherwise specified.

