**Table 2 Guidelines for FEV1 and/or FVC decrease**

Item	Parameter	Guideline
1	If FEV 1 and/or FVC $> 15\%$ decrease from the study baseline.	Repeat spirometry assessments preferably within 1 week See item 1a, 1b.
1a	If at repeat spirometry assessment: FEV 1 and/or FVC $> 15\%$ decrease from the study baseline.	Permanently discontinue study treatment and perform FU spirometry assessments.
1b	If at repeat spirometry assessment: FEV 1 and/or FVC $\leq 15\%$ decrease from the study baseline.	Resume regular spirometry assessment schedule. If at any other scheduled assessment FEV 1 and/or FVC $> 15\%$ decrease from the study baseline: permanently discontinue study treatment and perform FU spirometry assessment.

FEV1 = forced expiratory volume in 1 second; FVC = forced vital capacity; FU = follow-up.

If clinically significant, persistent respiratory AEs (e.g., dyspnea) are reported, PFTs must be performed and study treatment must be permanently discontinued. Further diagnostic work-up and consultation with a pulmonologist or other specialist should be considered according to local practice and the clinical situation.

In all cases of permanent study treatment discontinuation, follow-up monitoring must be provided until respiratory AEs are resolved and changes in pulmonary function are no longer clinically relevant or until medically indicated.

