### **11 STATISTICAL METHODS**

#### **11.1 General considerations**

All statistical analyses will be conducted by Actelion or by designated CROs supervised by Actelion.

The SAP for final analysis will be approved prior to database lock. The SAP for the interim safety review will be finalized prior to unblinding the study by the independent ISAC. The SAPs provide the full details of all analyses, data displays, and algorithms to be used for data derivations.

All data will be listed, and endpoints will be summarized by appropriate descriptive statistics (tables or figures), typically including:

- number of non-missing observations, number of missing observations, mean, standard deviation, median, Q1 (first quartile), Q3 (third quartile), minimum and maximum for continuous endpoints;
- number of non-missing observations, number of missing observations and frequency with percentage per category (percentages based on the number of non-missing observations) for categorical endpoints;
- number of subjects at risk, cumulative number of events, cumulative number of censored observations and Kaplan-Meier estimates of the survival function for time-to-event endpoints.

Baseline is defined as the last assessment prior to initiation of the study treatment.

Absolute changes from baseline are defined as: post-baseline value minus baseline value, i.e., a positive sign indicates an increase as compared to baseline.

A percentage (relative) change from baseline is defined as the absolute change from baseline divided by the baseline value (if the baseline value does not equal 0) multiplied by 100.

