## 10.8 Analysis of other efficacy variables

### 10.8.1.1 Exploratory disease activity endpoints

- Main analysis

For all the SLEDAI-2K variables (including number of affected joints) and the PGA variable [defined in Section 5.7.3.1], an ANCOVA model including baseline value as a covariate and treatment group as a factor is applied to the absolute change from baseline to EOT for each variable on the FAS and PPS. The difference in least squares means between each ACT-334441 dose and placebo is computed and the 95% confidence intervals for the differences are estimated.

- Secondary analysis

For the SLEDAI-2K (including number of affected joints) and PGA variables [defined in Section 5.7.3.1], separate summaries of quantitative descriptive statistics for absolute values, absolute change from baseline and percent change from baseline are presented by analysis visit and treatment group.

For modified SLEDAI-2K total score, the summaries are also presented stratified by baseline category (baseline total SLEDAI-2K score  $< 6$ , baseline total SLEDAI-2K score  $\geq 6$ , overall).

In addition, for the modified total SLEDAI-2K total score, the occurrence of an increase from baseline  $> 3$  is tabulated by analysis visit and treatment group.

The evolution of the values over time (PGA score, modified SLEDAI-2K score and number of affected joints) is provided in graphical format for each parameter from baseline to EOS visit (one figure per endpoint, one boxplot per treatment group and analysis visit).

All these analyses are performed on the FAS.

Listings are produced on the SCR. For PGA and SLEDAI-2K score, it displays the absolute values, the absolute change and the percent change from baseline to each post-baseline assessment, the values taken into account for the analysis are flagged.

In addition, for the modified SLEDAI-2K, the value at each analysis visit for each descriptor is included in a listing.

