#### **10.8.1.2 Exploratory biomarker**

For exploratory biomarkers [defined in Section 5.7.3.2], separate summaries of quantitative descriptive statistics for absolute values, absolute change and percent change from baseline are presented by analysis visit and treatment group (including geometric mean and associated 95% CI).

For exploratory biomarkers for which categories have been used, the number and percentage of subjects with a value in each category are summarized by analysis visit and treatment group.

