#### 10.9.6 Spirometry

Quantitative descriptive statistics are presented by parameter, by analysis visit and treatment group. In addition, a summary table presenting the absolute change from baseline to each visit up to EOS is produced. Similarly the percent change from baseline to each visit up to EOS are presented by visit and by treatment group.

The number and percentage of subjects with a decrease in FEV1 or FVC of > 15% from baseline value is provided for each visit, by analysis visit and treatment group, each with 95% Clopper-Pearson confidence intervals. In addition, the number and percentage of

subjects with a 15% decrease in FEV1 or FVC at one visit, 2 consecutive visits, 3 consecutive visits, and more than 3 visits during the treatment period is presented.

The evolution of the values over time is provided in graphical format for FEV1 (L), FVC (L) and FEV1/FVC (one figure per parameter: one boxplot per treatment group and analysis visit, from baseline to EOS).

All data (values and changes) are listed by treatment group, subject and visit. All marked abnormalities are flagged.

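### The SAP's default percentage denominator (all subjects in the analysis set) departs, undeclared, from the protocol's non-missing denominator and scales down the by-visit spirometry, SLEDAI-2K and biomarker percentages

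*SAP*

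**What the plan says.** Protocol 11.1 (General considerations) lists the usual summaries for categorical endpoints, including "frequency with percentage per category (percentages based on the number of non-missing observations) for categorical endpoints".

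SAP 10.2 (General rules for data presentations) sets a different default: "Denominators for percentages are the number of subjects in the pertinent analysis set and treatment group, unless otherwise specified". It also asks for the number of non-missing observations to be shown.

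The SAP departs from its default in some places. For ECG (10.9.3.1) and blood pressure (10.9.5), percentages are taken over subjects assessed after baseline within the interval concerned. For laboratory tests (10.9.4), they are taken over subjects with any post-baseline assessment. Adverse-event tables (10.9.1) have their own rule.

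Three by-visit displays have no such statement:

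- SAP 10.9.6: the number and percentage of subjects with an FEV1 or FVC fall above 15% "is provided for each visit, by analysis visit and treatment group, each with 95% Clopper-Pearson confidence intervals".
- SAP 10.8.1.1: an increase above 3 in the modified SLEDAI-2K total "is tabulated by analysis visit and treatment group". A percentage is not named here; it follows from the 10.2 rule for categorical variables.
- SAP 10.8.1.2: for categorised biomarkers, "the number and percentage of subjects with a value in each category are summarized by analysis visit and treatment group".

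SAP Section 4, which records changes and clarifications relative to the protocol, does not mention denominators.

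**The concern.** The two rules agree only when nobody is missing. The full analysis set is everyone randomized and the safety set is everyone dosed, so a subject with no value at a visit stays in the SAP denominator but cannot enter the numerator. The percentage therefore falls as missingness rises, whatever happened to the subjects who were measured. Arms with different amounts of missing data are scaled by different factors.

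Some missingness comes from the design. Under Protocol 5.1.9, a subject who stops treatment early is asked back for the EOT and EOS visits, not for the remaining on-treatment visits.

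Safety is a main objective, and the FEV1/FVC fall above 15% is a named safety endpoint. SAP 4.3.2 added the SLEDAI-2K increase above 3 in order to describe flares. With 12 subjects per active arm, each missing subject moves the printed figure visibly. The spirometry table has the same by-visit, Clopper-Pearson layout as the ECG and blood pressure tables, yet a different denominator, and no reason is given.

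**Working it through.** The documents print no percentage that depends on this rule, so there is no figure to reproduce. The check compares the two rules directly.

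**Inputs from the documents.** Planned group sizes are N=12 per active dose and N=16 for pooled placebo (Protocol 11.6.1). The interval is the two-sided 95% Clopper-Pearson interval of SAP 9.1.1, whose n is the number of subjects in the group. The only loss figure given is 10% excluded from the PD analysis set (Protocol 11.6.1). That is at best a rough guide to missingness at a visit: 0.10 × 12 = 1.2, or about 1 subject per active arm.

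**Assumptions.** The number missing at the visit, m = 1 to 4, and the number of events, e = 2.

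**Formulas.** SAP rule: e/N. Protocol rule: e/(N-m). Their ratio is (N-m)/N, which does not depend on e.

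**Active arm, N=12, e=2.** The SAP rule gives 2/12 = 16.7% (95% CI 2.1 to 48.4) for every m.

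| Missing | Protocol rule | 95% CI | Ratio (N-m)/N |
|---|---|---|---|
| 1 | 2/11 = 18.2% | 2.3 to 51.8 | 0.917 |
| 2 | 2/10 = 20.0% | 2.5 to 55.6 | 0.833 |
| 3 | 2/9 = 22.2% | 2.8 to 60.0 | 0.750 |
| 4 | 2/8 = 25.0% | 3.2 to 65.1 | 0.667 |

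**Pooled placebo, N=16, e=2.** The SAP rule gives 2/16 = 12.5%. The protocol rule gives 2/15 = 13.3% up to 2/12 = 16.7% for 1 to 4 missing, with ratios from 0.938 to 0.750.

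**Unequal missingness.** Suppose placebo is complete with 3 events, 3/16 = 18.8%, and an active arm has 2 events with 3 of 12 missing. The SAP rule prints 16.7% for the active arm, below placebo. The protocol rule gives 22.2%, above placebo. The order reverses, although with these numbers neither difference means much.

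**Interval.** Of the three displays, only spirometry carries one. With 2 events and 3 missing, the printed upper limit is 48.4% rather than 60.0%, because the interval takes credit for three subjects who were not measured.

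**Biomarker categories.** A missing subject is in the denominator and in no category, so the category percentages sum to (N-m)/N. With 3 of 12 missing they sum to 75%.

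**The case against.** There is a fair case that this is minor.

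- Protocol 11.1 introduces its list as what summaries typically include and leaves full detail to the SAP, so a SAP may choose another denominator. That stands as permission. It does not explain why the change is undeclared, or why spirometry differs from ECG and blood pressure.
- SAP 10.2 prints the non-missing count, so a reader can recompute the percentage. True, but the printed percentage and the spirometry interval still follow the wrong n.
- Stopping treatment is not leaving the study. EOT and EOS visits include spirometry and SLEDAI-2K, Protocol Table 2 requires follow-up spirometry after a confirmed fall, and SAP 11.1.1 assigns unscheduled assessments to visit windows. The LOCF end-of-treatment record in SAP 11.1.1 largely protects that row. This reduces the missing data; it does not protect the observed by-visit rows.
- With 1 of 12 missing, the level closest to the only loss figure given, the gap is 18.2% against 16.7%, or 1.5 points.

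A reader might infer more than the documents support. One inference is that a subject stopped for a confirmed FEV1 fall (Table 2: "Permanently discontinue study treatment and perform FU spirometry assessments") has the fall hidden at later missed visits, and that the protocol denominator would restore it. It would not. If that was the only fall, a later missed visit shows 0/12 under one rule and 0/11 under the other. That loss is informative dropout, not a denominator error. The event is also counted elsewhere: SAP 10.9.6 tabulates falls at one, two, three and more visits, and adverse events leading to discontinuation have their own tables.

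A second inference is that the high doses are affected most. The documents give no discontinuation rates by dose. A third is that missing biomarker subjects are treated as event-free. They fall in no category at all.

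**Conclusion.** The point holds as a conflict between the two documents with a definite numerical effect. As written, the SAP multiplies each observed by-visit percentage in the three displays by (N-m)/N relative to the protocol rule, and it gives the spirometry interval too large an n. The factor is exact. The size in this trial depends on how many subjects are missing at each visit, which the documents do not say. From 1 to 4 missing of 12, the factor runs from 0.92 to 0.67.

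The protocol's percentage is the rate among subjects still assessed. It equals the rate for the whole arm only if missingness is unrelated to outcome, so it should not be called unbiased.

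The conclusion assumes that no table shell sets another denominator; SAP Section 13 shows no table list in the available text. The affected tables are exploratory or descriptive. The main pharmacodynamic test, the sample size, the power and the stopping rules do not use them. It is worth correcting before the tables are produced, but it does not threaten the main result.

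**What to change.** Add one sentence to SAP 10.2, or to 10.8.1.1, 10.8.1.2 and 10.9.6: by-visit percentages, and any confidence intervals on them, use the subjects with a non-missing assessment at that visit and, where the criterion is a change from baseline, a non-missing baseline. Keep the analysis-set denominator for disposition, medical history, medication and adverse-event tables. If the sponsor prefers the current default, declare the departure from Protocol 11.1 in SAP 4.1 with a reason.

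Add a footnote that by-visit rates describe assessed subjects only, and point to the spirometry summary by number of visits with a fall and to the whole-period abnormality summaries, since the new denominator does not deal with informative dropout.

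The cost is a sentence in the SAP and a denominator change in three sets of table shells. No extra data are needed.
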